6.4 Sample Size and Power

The primary outcome variable will be Informed Decision-Making, assessed at the 6-month follow-up. Our targeted sample size will be 300 (75 in each of the four study arms). Power analyses performed a priori indicated that a sample of this sample size would provide 80% power to detect a between-group difference of 25% in the percentage of participants classified as meeting the criteria for informed decision-making (e.g., 60% versus 35% among individuals assigned to the DrugFactsBox[®] versus Other CMI groups, respectively). This anticipated effect size was based on that observed in previous studies⁵⁵ and corresponds to a slightly smaller than moderate sized effect using the criteria developed by Cohen.⁸⁶ These power calculations were performed with

alpha (2-tailed) set at 0.05 and allowed for 15% attrition from baseline to final follow-up.

6.5 Interim Analysis

Not applicable

7 STUDY INTERVENTION (drug, device or other intervention details)

The investigators will evaluate the effectiveness of two separate interventions: the DrugFactsBox[®] format (compared to Other CMI, primarily Medication Guides) and gist reasoning training delivered via the SMART Program (compared to standard care). Each intervention is described below.

DrugFactsBox[®] Format. The original DrugFactsBox[®] format consisted of a standardized 2-page summary that followed plain language guidelines and best practices to enhance comprehension among individuals with limited literacy or numeracy skills.^{87,88} Research involving nationally representative samples has demonstrated that the DrugFactsBox[®] format improves (1) patient comprehension of medication risks and benefits and (2) patient judgment and decision-making.⁸⁸⁻⁹⁰ To produce Drug Facts Boxes, information from FDA drug approval documents and systematic reviews published in the scientific literature are examined to extract information concerning drug benefits and harms, as well as areas of scientific uncertainty that are not always conveyed clearly to the general public. The information extracted is used by medical experts to create a Drug Facts Box. Each section in a Drug Facts Box is clearly labeled and provides quantitative information concerning the drug's potential benefits and harms in comparison to treatment alternatives or no treatment (if data are from a placebo-controlled trial). This type of quantitative information concerning potential benefits and harms is missing from FDA-approved medication guides and other types of CMI commonly given to patients in the United States when prescriptions are dispensed.

For this study, the investigators will create a website that contains 16 Drug Facts Boxes for those medications most commonly used to treat RA in the United States (i.e., abatacept, adalimumab, certolizumab, etanercept, golimumab, hydroxychloroquine, infliximab, leflunomide, methotrexate pill, methotrexate shot, prednisone, rituximab, sulfasalazine, tocilizumab infusion, tocilizumab shot, and tofacitinib). A pill bottle icon for each of these medications will appear on the website landing page. When the icon for a medication is clicked, an overview of the medication will appear. The overview will include a section labeled *Bottom Line* which contains a narrative summary of potential medication benefits and harms, emphasizing bottom-line gist. The overview page will also provide links to other pages within the website that contain additional information about the medication. These links will be labeled: Trials, Side Effects, How to Use, Lifestyle Changes, and Interactions. The Trials page will provide quantitative information

concerning potential medication benefits and harms, mirroring the original DrugFactsBox[®] format.

Effects of the DrugFactsBox[®] format will be evaluated in comparison to other types of written CMI. All participants assigned to receive Other CMI will be given access to a website that contains CMI for the same 16 medications listed above. For medications that have an FDA-approved Medication Guide (i.e., abatacept, adalimumab, certolizumab, etanercept, golimumab, infliximab, rituximab, tocilizumab infusion, tocilizumab shot, and tofacitinib), the website will provide a link to the Medication Guide. For the remaining medications (i.e., hydroxychloroquine, leflunomide, methotrexate pill, methotrexate shot, prednisone, and sulfasalazine), the website will provide a link to CMI developed by the American Society of Health-System Pharmacists[®]. These materials are similar to the CMI that is given to patients in the United States when prescriptions are dispensed. The DrugFactsBox[®] website and the Other CMI website will both allow participants to print a hard copy of the materials, if desired.

Because federal law mandates that Medication Guides be given to patients when certain medications are dispensed, the investigators view them as a component of usual care. Nonetheless, the investigators are aware of no research demonstrating that the Guides improve patient-centered health outcomes. Moreover, research suggests that many patients have difficulty understanding and using the information contained in the Guides.^{31-35,91} Comprehension of information contained in the Guides is particularly low among older patients and those with limited health literacy.^{32,33}

SMART Program. The SMART Program was designed to enhance gist reasoning ability by training participants on the use of three metacognitive strategies: Strategic Attention (e.g., ignoring or eliminating distractions to facilitate single-minded focus on understanding the specific topic at hand, prioritizing health issues/problems with greatest impact on daily function, understanding signs and symptoms of brain fatigue and taking mental breaks to recharge), Integrated Reasoning (e.g., strengthening integrative mental capacity to synthesize general as well as medical information from multiple sources), and Innovation (e.g., examining multiple perspectives and information sources to best understand the information at hand, comparing and contrasting information to help determine the best decision, asking insightful questions that involve considering information from differing perspectives).⁹² In randomized controlled trials, the SMART Program has been shown to strengthen gist reasoning ability especially as evidenced in efficient synthesis and comprehension of complex information encountered in everyday life such as news articles and medical information.^{60,92-94} Evidence has also demonstrated generalized benefits of improved performance on cognitive, neural and functional measures immediately post training and 3-6 months post-training.⁹² Thus, considerable evidence supports the effectiveness of the SMART program in enhancing gist reasoning ability. However, this will be the first

study to examine whether the program enhances patient ability to understand written prescription drug information and whether better understanding translates into improved decision-making and health outcomes.

Effects of the SMART Program will be evaluated in comparison to standard care. Because participants will be recruited from multiple, geographically diverse sites, the investigators will not attempt to measure the content of care received. However, because the type of gist reasoning training provided by the SMART Program is very innovative, the investigators believe that it is unlikely that any participants in the comparison group had access to similar programs.

8 STUDY INTERVENTION ADMINISTRATION(if applicable)

Participants will be randomized to study arm on a 1:1:1:1 basis. Prior to the start of participant recruitment, the principal investigator will generate a random allocation sequence using PC-SAS® (version 9.4). Random numbers will be generated in blocks of 20 to ensure balance across the four study groups over the entire course of data collection. The random number sequence will be imported into the REDCap tracking database used by the project director, working out of the UNC-Chapel Hill office, to record the name and contact information for study participants as they are enrolled in the study. To ensure allocation concealment, the REDCap database will be programmed so that the group assignment variable: (1) cannot be viewed until after the patient contact information has been entered and (2) cannot be changed after the patient contact information has been entered. All personnel involved in data collection and delivery of the SMART program were blinded to participant group assignment. Because the study involves minimal risk, the investigators have no plans to unblind participants or study personnel. However, participants will be encouraged to report any problems they experience to the research staff so that unanticipated problems might be identified.

Immediately following completion of baseline data collection, participants will be emailed a link to either the DrugFactsBox® website or the Other CMI website, depending on the group to which they will be randomized. To track website utilization, participants will be assigned a unique username that they will be required to enter each time they visited the website. Participants will be free to access the site whenever they chose and will have access to the site from the time their username is assigned until the end of the study. At the conclusion of the study, tracking data will be downloaded and used to assess how often each participant visited the website and the specific pages viewed.

Participants randomized to the SMART Program will be contacted by staff at the Center for BrainHealth at the University of Texas at Dallas following completion of baseline data collection, by email and telephone, to enroll them in the next SMART Program. The

program will be delivered by Center research personnel certified to provide the program using an online video conferencing platform that permits synchronous, audio and visual communication between trainers and participants. Participants will only need a computer or mobile phone with internet access to participate. Initially, the program will be delivered via four 60 to 90 minute sessions, spanning a one month period. In most cases, the program will be delivered in small groups with three to four participants. However, the program will be delivered one-on-one, if needed to accommodate participant schedules.

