Study Design	The study will use a randomized controlled trial design, with four study arms. Data will be collected primarily via telephone interviews, and self-administered, Internet-based surveys using REDCap and Qualtrics. All participants will be followed for 6 months after the completion of baseline data collection.
Subject Population key criteria for Inclusion and Exclusion:	
Inclusion Criteria
 
 1. Subjects age 18 years and older 2. Subjects with physician-confirmed rheumatoid arthritis or similar type of inflammatory arthritis 
Exclusion Criteria
 
 1. Subjects who do not speak English 2. Subjects who do not have access to the internet and a working email address 3. Subjects who are not eligible for DMARD therapy 4. Subjects who have health problems (e.g., active cancer, planned surgery) that prevent changes in their medication regimen
Number Of Subjects	The targeted sample size is 300.
Study Duration	Each subject's participation will last 6 months. The entire study is expected to last 3 years.
Study Phases Screening Study Treatment Follow-Up	
 (1) Screening: screening for eligibility and obtaining consent (2) Baseline data collection: Telephone interview and internet-based self-administered questionnaire (3) Intervention delivery: Given access to written medication information immediately following baseline. Completion of SMART training usually requires one to three months (4) Follow-Up data collection: Three follow-ups, conducted 6 weeks, 3 months, and 6 months following completion of baseline data collection
Efficacy Evaluations	The primary outcome variable is informed decision making regarding use of DMARDs. Participants will be classified as meeting the criteria for informed decision making if they: (1) have adequate knowledge, have values that favor use of medications to control disease activity, and are using a DMARD OR (2) Have adequate knowledge, have values indicating reluctance to use medications to control disease activity, and are not using a DMARD. All other individuals will be classified as not meeting the criteria for informed decision-making.

Pharmacokinetic Evaluations	Not applicable
Safety Evaluations	Not applicable

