In the main analysis, the investigators will use an *intention-to-treat* strategy, with individuals included in the analysis based on random group assignment, without regard to whether they were actually exposed to the intervention. However, the investigators will only include participants with nonmissing data at the 6-month follow-up. In addition to the main analyses, the investigators will perform three sets of sensitivity analyses to

assess the robustness of the findings. The first set of sensitivity analyses will use an *as-treated* approach and include only people with nonmissing data at the 6-month follow-up. Individuals will be included in this analysis only if they actively participated in the interventions. For the DrugFactsBox[®]/Other CMI groups, the investigators defined active participation as viewing at least one page on the DrugFactsBox[®]/Other CMI website. For the SMART group, the investigators will define active participation as attending at least 3 of the 4 training sessions. Note that all individuals in the No SMART group will be included in the *as-treated* analyses because they will not have an opportunity to participate in any training. In the second set of sensitivity analyses, the investigators will use an *intention-to-treat* approach and impute missing data using the last-observation-carried forward method for individuals who do not complete the 6-month follow-up. In the final set of sensitivity analyses, the investigators will use as *as-treated* approach and impute missing data using the last-observation-carried forward method.

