Secondary Analyses: The investigators will use the same analytic strategy to examine the effect of the intervention on 18 secondary outcomes assessed at the 6-month follow-up: Medication Self-Management Knowledge, Selective Learning, Complex Abstraction, Lesson Quality, Use of the RA Self-Management Website, Participation in the BetterChoices,BetterHealth program, Self-Efficacy, Overall Medication Satisfaction, Global Treatment Satisfaction, Medication Adherence, Objective Health Literacy, Subjective Health Literacy, Disease Activity, Illness Intrusion, Illness Distress, Global Health, Depression, and Fatigue. In these analyses, the investigators will use either logistic or linear regression, depending on the measurement properties of the outcome variable. Due to the number of endpoints examined in these secondary analyses, the investigators will use the Hochberg method to adjust for the potential inflation of Type I error.⁸⁵

Exploratory Analyses: The investigators will use the same analytic strategy to evaluate intervention effects at the 6-week and 3-month follow-ups. However, these analyses will be considered exploratory and are designed to capture any transient intervention effects that may occur.

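### The as-treated sets put no date limit on exposure, so a first page view after the outcome assessment can count as treatment for that outcome

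*Combined protocol and SAP*

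**What the plan says.** Section 6.3 plans a main intention-to-treat analysis and three sets of sensitivity analyses. Two of the three are as-treated: "The first set of sensitivity analyses will use an *as-treated* approach and include only people with nonmissing data at the 6-month follow-up", and the last set repeats the approach with the last observation carried forward. For the website factor, "the investigators defined active participation as viewing at least one page on the DrugFactsBox[®]/Other CMI website". For SMART the threshold is 3 of the 4 sessions. Neither threshold carries a date.

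Section 8 describes how page views are recorded: "To track website utilization, participants will be assigned a unique username that they will be required to enter each time they visited the website". On the length of access, it says that each person "will have access to the site from the time their username is assigned until the end of the study". On the download, it states: "At the conclusion of the study, tracking data will be downloaded and used to assess how often each participant visited the website". The synopsis (Study Duration) gives each subject 6 months of participation but says of the whole trial: "The entire study is expected to last 3 years".

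Under Exploratory Analyses, section 6.3 adds: "The investigators will use the same analytic strategy to evaluate intervention effects at the 6-week and 3-month follow-ups". The synopsis (Study Phases) says that SMART training is usually completed in one to three months.

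**The concern.** An as-treated analysis asks what happened among people who had received the intervention when the outcome was measured. Exposure after the assessment cannot have influenced it. With an undated threshold and a log that stays open beyond the 6-month visit, a participant who had seen nothing by 6 months can still qualify through a later visit. Such people are expected to pull the as-treated contrast toward the contrast among the unexposed, although that direction is not guaranteed.

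Entry to the set would also depend partly on enrolment date, because early enrollees have longer to qualify. The stakes are limited to the two as-treated sets at 6 months and to any as-treated results at 6 weeks and 3 months.

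**Working it through.** **The plan's own figure.** The only reproducible design figure is the power in section 6.4: 60% versus 35%, two-sided alpha 0.05, 75 per arm, 15% attrition. With 75 x 0.85 = 63.75 completers per arm, z = [0.25 x sqrt(63.75) - 1.96 x sqrt(2 x 0.475 x 0.525)] / sqrt(0.60 x 0.40 + 0.35 x 0.65) = (1.996 - 1.384)/0.684 = 0.895. Power is 81.5%, against 80% stated, for one arm versus one arm. The point does not depend on this; the 25-point difference is used below only as a scale.

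**Step 1: exposure window.** Window = study end minus enrolment date. With a 36-month study (synopsis) and enrolment over months 0 to E (E is assumed):

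- E = 30: 6 to 36 months
- E = 24: 12 to 36 months
- E = 18: 18 to 36 months

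With a cut-off at the outcome, every participant's window is 6 months.

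**Step 2: late first views among 6-month non-viewers (assumed rates).** Suppose non-viewers first open the site at a constant rate h of 0.5% to 2% per month after month 6. For enrolment month e, the share that does so by month 36 is 1 - exp(-h(30 - e)), averaged over e uniform on (0, E).

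- Low end, h = 0.005, E = 30: 1 - (1 - exp(-0.15))/0.15 = 0.071
- High end, h = 0.02, E = 18: 1 - (exp(-0.24) - exp(-0.60))/0.36 = 0.339

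The range is 7% to 34%.

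**Step 3: share of the as-treated set.** Let u be the proportion with no view by 6 months (assumed 10-30%) and v the share of those who view later. Applying the website criterion alone to all completers, misclassified share = uv/(1 - u + uv).

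- u = 0.10, v = 0.07: 0.007/0.907 = 0.8%
- u = 0.30, v = 0.34: 0.102/0.802 = 12.7%

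Among 300 x 0.85 = 255 completers, that is about 2 to 26 people (255 x 0.007 = 1.8; 255 x 0.102 = 26.0).

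**Step 4: effect on the contrast.** If late viewers show no effect, a 25-point difference becomes 25 x (1 - 0.008) = 24.8 or 25 x (1 - 0.127) = 21.8 points.

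**Step 5: SMART at 6 weeks.** Six weeks is 1.38 months. Assume completion time T is uniform on 1 to 3 months from baseline, among those who eventually attend at least three sessions.

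- Third session 0.25 to 0.33 month before completion: (1.38 + 0.25 - 1)/2 = 31% to (1.38 + 0.33 - 1)/2 = 36%
- Sessions spread evenly over T, third at 3/4 T or 2/3 T: (1.38/0.75 - 1)/2 = 42% to (1.38/0.667 - 1)/2 = 53%

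So 31% to 53% would have had a third session by 6 weeks. Under the same assumption all would have had it by 3 months.

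**The case against.** Section 6.3 does not name the end-of-study download as the source for active participation, and one download at the end does not stop the analyst from filtering by date. The end of the study could also mean the end of each participant's follow-up. These objections are fair, but they do not settle the matter. The username log is the only page-view source described for these two websites. The synopsis separates 6 months per subject from 3 years overall, and no section states a cut-off. The participant-level reading would also leave the 6-week and 3-month question open.

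The size objection largely stands. One page view suffices, so only first views after the outcome matter. Participants are directed to the site after randomisation and emailed the link straight after baseline, so late first views may be uncommon.

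A reader might infer more than the documents support:

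- With an assumed enrolment period of 18 to 30 months, 71-78% of tracked time falls after the 6-month outcome. This does not measure misclassification, because further visits by someone who has already viewed a page change nothing.
- The last enrollee has about 6 months in which to qualify. That holds only with 30-month enrolment; with 18-month enrolment it is 18 months.
- Unequal windows bias the comparison between arms. Randomisation in blocks of 20 should balance enrolment date across arms, so unequal windows alone create no arm imbalance.
- Two-thirds of SMART attenders are untreated at 6 weeks. That depends on one assumption about session spacing.

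The 6-week point also requires that the shared analytic strategy for the exploratory analyses includes the as-treated sets, which section 6.3 does not say outright. Incomplete training at 6 weeks affects the intention-to-treat estimate too, but there it is a feature of design timing, not a misclassification.

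**Conclusion.** The gap is real and limited. As written, the as-treated rule can admit people first exposed after the outcome. The primary intention-to-treat analysis is untouched. At 6 months SMART is essentially unaffected, given the stated completion time, and the website effect is probably small: 0.8-13% of the as-treated set. That range rests wholly on assumed visit rates and on applying the website criterion to everyone. The shrinkage of 25 points to 24.8-21.8 further assumes no effect among late viewers.

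If the as-treated sets are carried to 6 weeks, the gap is larger: under uniform completion, roughly half to two-thirds of the SMART participants counted as treated (47-69%, the complement of 31-53%) would not yet have had a third session. The point deserves a correction before analysis, so that the cut-off is not chosen with results in view.

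**What to change.** In section 6.3, define active participation separately for each time point: count only page views and SMART sessions dated on or before that participant's outcome assessment being analysed. For last-observation-carried-forward values, use the date of the carried observation. In section 8, apply the same limit to the log data used for this purpose, and confirm that the log records visit dates, which the documents do not state. Also say whether the exploratory 6-week and 3-month analyses include the as-treated sets.

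If events are dated, the cost is a sentence or two and a date filter. The as-treated sets become slightly smaller at 6 months. Anyone whose baseline value is carried forward could not meet the website or SMART criterion, since access starts after baseline; the plan should acknowledge this. At 6 weeks the SMART as-treated set could shrink substantially and keep only early completers, while the No-SMART participants face no equivalent restriction. That is a selection effect, so those results should be labelled as applying to early completers.
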